## 5. TREATMENT PLAN

### 5.1. Phase 1 Dose Administration

#### 5.1.1. Study Treatment

The orally administered film-coated tablet formulation of DS-1594b will be supplied by Daiichi Sankyo and are in 20 mg, 50 mg, and 200 mg dose strengths.

The first dose cohort will start at 70 mg twice daily, approximately every 12 hours. For provisional dose levels beyond the first dose cohort, see [Figure 1](#)[Figure 1](#). Alternative doses or dosing regimens may be enrolled based on emerging clinical data, including intermediate dose levels or dose de-escalation. BID and QD cohorts can be enrolled in parallel and will be evaluated independently for DLT.

Formatted: C-Hyperlink

#### 5.1.2. Dose Administration Guidance

DS-1594b will be administered orally on a continuous twice daily (or once daily) regimen. In this study a complete cycle of treatment is defined as 28 days. The Investigator must instruct the subject to take the study drug (DS-1594b) exactly as prescribed:

1. For BID dosing, subjects should take DS-1594b tablets twice daily at approximately the same time each day for morning and evening doses; for QD dosing, subjects should take DS-1594b tablets once daily at approximately the same time each day for morning doses.
2. Each dose of DS-1594b is to be taken with a glass of water (at least 8 ounces – approximately 250 mL) and consumed over as short a time as possible (i.e., not slower than 1 tablet every 2 minutes).
3. Subjects should be instructed to swallow the tablets whole and not to chew them.
4. DS-1594b should be administered under fasting condition, at least 1 hour before or 2 hours after a meal.
5. For BID dosing, the morning and evening doses should be taken 12 ( $\pm$  4) hours apart, although 12-hour interval is recommended. If a dose is not taken within 4 hours of the planned dosing time, the missed dose should not be replaced. On days when serial PK

blood samples are to be collected especially those with 12 hours post-dose timepoint (see Section 8.4.1), subjects should keep the 12-hour interval between morning and evening doses.

6. On days when PK blood samples are to be collected, subjects will be instructed to hold their dose until arrival at the study center; the site will remind subjects one day before not to take the morning dose at home. DS-1594b will be administered at the site in the morning after the pre-dose ECG assessment and PK blood draw and prior to the post-dose PK blood draws. The exact date/time of drug administration should be recorded in the eCRF. If a subject vomits within the first 4 hours post-treatment on a full PK sampling day, the exact time of vomiting should be recorded on the eCRF.
7. All pre-dose PK samples should be drawn just before DS-1594b dosing. The sampling time of the pre-dose PK sample and the dosing time of DS-1594b must be precisely recorded in the eCRF. Furthermore, the dosing time of DS-1594b on the previous day must be precisely recorded in the eCRF.

**DDI sub-study only:**

- On days with posaconazole co-administration, DS-1594b will be dosed first under fasting condition. One hour later, posaconazole will be dosed (within 0.5 hours) following a breakfast.
- On days with voriconazole co-administration, DS-1594b and voriconazole can be administered together since both drugs will be given under fasting conditions.

**Food effect sub-study only:**

- Subjects in this sub-study do not follow bullet (4) above but the bullets below for prandial condition.
- For the morning doses from Cycle 1 Day 1 to Cycle 1 Day 8, DS-1594b will be administered immediately (within 0.5 hours) following a standard breakfast defined as one containing 600 kcal and 30% fat (~ 21g fat). Subjects should refrain from food and drink, except water, for at least 2 hours after dosing; for the evening doses (12 hours apart from morning dose) (applicable for BID dosing only), DS-1594b will also be administered immediately (within 0.5 hours) following a standard dinner (same meal content as breakfast). Subjects should refrain from food and drink, except water, for 2 hours before dosing (except for breakfast and dinner) and for 2 hours after dosing.
- Starting from Cycle 1 Day 9 to Cycle 1 Day 18, DS-1594b should be administered under fasting condition (i.e. subjects should refrain from food and drink, except water, for 2 hours before dosing and for 2 hours after dosing). After completion of the sub-study (Cycle 1 Day 18 is the last day of sub-study), subjects will continue with DS-1594b dosing under fasting conditions, same as patients not in the food effect sub-study (DS-1594b dosing at least 1 hour before or 2 hours after a meal) starting on Cycle 1 Day 19.

## 5.2. Phase 2 Cohort A: R/R AML with MLL-rearrangement

### 5.2.1. Dose Administration Guidance

The general dose administration guidance for DS-1594b as listed in Section 5.1 should be followed.

## 5.3. Phase 2 Cohort B: R/R AML with NPM1 mutation

### 5.3.1. Dose Administration Guidance

The general dose administration guidance for DS-1594b as listed in Section 5.1 should be followed.

## 5.4. Phase 2 Cohort C: R/R AML Treated with the Combination of Azacitidine and Venetoclax with DS-1594b

### 5.4.1. Study Treatment of Study Drug and Other Combination Drugs

Subjects will be treated according to the following dose levels;

**Table 6: Dose Levels for Azacitidine, Venetoclax, and DS-1594b**

Dose Level	Azacitidine (mg/m  )	Venetoclax (400 mg or equivalent)	DS-1594b
-1	75 mg/m  D1-7	D1-28 a, b, c, d	Lower dose of DS-1594b as recommended by SRC
0 (Starting dose)	75 mg/m  D1-7	D1-28 a, b, c, d	One dose level below the RP2D of DS-1594b from Phase 1
1	Not applicable	Not applicable	RP2D of DS-1594b from Phase 1

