**Table 1: Primary Objectives and Their Endpoints and Category**

Primary Objectives	Endpoints	Category
Phase 1 only: To determine the safety, tolerability, Maximum Tolerable Dose (MTD), and Recommended Phase 2 Dose (RP2D) of DS-1594b in subjects with relapsed/refractory (R/R) Acute Myeloid Leukemia (AML) and Acute Lymphoblastic Leukemia (ALL).	MTD; RP2D; Safety Profile of DS-1594b;	Safety
Phase 2 only (Cohort A): To evaluate the safety, tolerability, and efficacy defined as Complete Remission (CR) and Complete Remission with Partial Hematologic Recovery (CRh) rate of DS-1594b in subjects with R/R AML with Mixed-Lineage Leukemia rearrangement (MLLr).	CR/CRh rate with DS-1594b monotherapy in R/R AML with MLLr; Safety Profile of DS-1594b	Efficacy Safety
Phase 2 only (Cohort B): To evaluate the safety, tolerability, and efficacy defined as CR+CRh rate of DS-1594b in subjects with R/R AML with a Nucleophosmin 1 mutation (NPM1m).	CR/CRh rate with DS-1594b monotherapy in R/R AML with NPM1m; Safety Profile of DS-1594b	Efficacy Safety
Phase 2 only (Cohort C): To evaluate the safety, tolerability, and efficacy defined as CR+CRh rate of DS-1594b in combination with azacitidine and venetoclax in R/R MLLr or R/R NPM1m AML.	CR/CRh rate with DS-1594b monotherapy in R/R AML with MLLr; Safety Profile of DS-1594b in combination with azacitidine and venetoclax	Efficacy Safety
Phase 2 only (Cohort D): To evaluate the safety, tolerability, and efficacy defined as CR+ Complete Remission with Incomplete Hematologic Recovery (CRI) rate of DS-1594b in combination with mini-HCVD in R/R ALL with MLLr.	CR/CRI rate with DS-1594b in combination with mini-HCVD in R/R ALL with MLLr; Safety Profile of DS-1594b in combination with mini-HCVD	Efficacy Safety

Response definitions Section [8.8](#)

Protocol 2020-0946  
20 Aug 2021  
Version 5.0

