## 3.3. Phase 2 Design

Enrollment in Phase 2 will start once the RP2D has been determined in Phase 1. This Phase 2 study will have four cohorts:

- Cohort A: DS-1594b monotherapy for R/R AML with MLL-r,
- Cohort B: DS-1594b monotherapy for R/R AML with NPM1m,
- Cohort C: DS-1594b in combination with azacitidine and venetoclax for R/R AML with NPM1m or MLLr
- Cohort D: DS-1594b in combination of mini-HCVD for R/R ALL with MLLr

Subjects enrolled in Cohorts A and B will receive the RP2D dose of DS-1594b determined in Phase 1. Cohorts C and D will enroll an initial 6 subjects in a safety run-in at one dose level below the RP2D (Dose level 0) with DS-1594b dose titration as specified below.

Cohorts A and B (single agent cohorts) will enroll a maximum of 26 subjects, and Cohorts C and D (combination cohorts) will enroll a maximum of 32 subjects, to allow reasonable determination of CRc within 3 months of therapy initiation.

For the combination cohorts (C & D) there will be a safety-run in evaluation with pre-defined toxicity stopping rules to be implemented for early DLT evaluation as per following plan:

- Safety run-in evaluation by the Safety Review Committee of the first 6 subjects in cohorts C and D will occur after 6 subjects have completed at least one cycle of treatment (or at least 28 days from the first day of treatment).
- Enrollment will be paused while the first 6 subjects are evaluated for safety. Each combination cohort will be evaluated independently.
  - If  $\leq 1$  of the 6 subjects experiences DLT in the first cycle of treatment, the treatment combination will be considered as safe and the DS-1594b dose can be escalated to the RP2D (Dose level 1) for the treatment of the next 6 patients (repeat the safety run-in evaluation). If the RP2D (Dose level 1) is considered safe, continue enrollment of an additional 20 subjects at the RP2D (i.e. total subjects treated at the RP2D will be 26 subjects; total cohort size will be 32 subjects). If  $\geq 2$  of 6 subjects at the RP2D experiences DLT in the first cycle of treatment, de-escalate and continue enrollment of an additional 20 subjects at Dose Level 0.

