**Table 7: Dose levels for miniHCVD, and DS-1594b**

Dose Level	miniHCVD	DS-1594b
-1	As published  miniHCVD regimen	Lower dose of DS-1594b as recommended by SRC
0 (Starting dose)	As published miniHCVD regimen	One dose level below the RP2D of DS-1594b from the Phase 1
1	Not applicable	RP2D of DS-1594b from the Phase 1

DS-1594b orally twice daily (or daily, dependent on results from dose escalation phase). In each cycle, DS-1594b will be taken daily continuously.

Variations in dose reductions of the individual chemotherapy or the administration of venetoclax or supportive care dose schedules other than those suggested below are allowed in the best interest of subjects. Such subjects should be discussed with the principal investigator. Dose escalations of chemotherapy above those outlined in the protocol; however, are not allowed. Variations in infusion times due to minor differences in IV bag overfill/underfill and institutional procedure on flushing chemotherapy lines will not result in protocol deviation.

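### Tables 6 and 7 mark the backbone drugs as not applicable at Dose Level 1, against Section 3.3; separately, Table 1 gives Cohort C the Cohort A efficacy endpoint

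*Combined protocol and SAP*

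**What the plan says.** **Dose-level tables.** Sections 5.4.1 and 5.5 present Tables 6 and 7 as the levels by which subjects are treated. At levels -1 and 0, Table 6 lists azacitidine 75 mg/m² on Days 1–7 and venetoclax on Days 1–28 with footnotes a to d; Table 7 lists the published mini-HCVD regimen. At Dose Level 1 the DS-1594b column reads "RP2D of DS-1594b from Phase 1" in Table 6 and "RP2D of DS-1594b from the Phase 1" in Table 7. Every backbone cell in those two rows reads "Not applicable", and no footnote is attached.

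**Section 3.3.** The combination cohorts are defined without reference to dose level: "Cohort C: DS-1594b in combination with azacitidine and venetoclax for R/R AML with NPM1m or MLLr" and "Cohort D: DS-1594b in combination of mini-HCVD for R/R ALL with MLLr". If Dose Level 0 passes its run-in, "the treatment combination will be considered as safe and the DS-1594b dose can be escalated to the RP2D (Dose level 1"). The run-in is then repeated in the next 6 subjects. If that also passes, 20 more are enrolled: "total subjects treated at the RP2D will be 26 subjects; total cohort size will be 32 subjects". Section 5.5.1 sends Cohort D back to Section 3.3 for this step.

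**Table 1.** The Cohort C objective is the combination with azacitidine and venetoclax in MLLr or NPM1m AML. The endpoint cell in the same row reads "CR/CRh rate with DS-1594b monotherapy in R/R AML with MLLr; Safety Profile of DS-1594b in combination with azacitidine and venetoclax".

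**The concern.** A dosing table and the design section describe Dose Level 1 differently. Taken at face value, the tables show DS-1594b with no backbone at the level where, on the planned path, most of each combination cohort is treated. Section 9.3 monitors up to 26 subjects per cohort and leaves out the first 6 run-in subjects in Cohorts C and D. On the planned path, those 26 are exactly the Dose Level 1 subjects.

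Table 6 has a practical gap too. Footnotes a to d cover venetoclax ramp-up, Cycle 1 duration, later-cycle duration and the interaction with DS-1594b, but they are attached only to levels -1 and 0. Footnote d allows the venetoclax and DS-1594b levels to be adjusted after the run-in data are reviewed. Dose Level 1 follows the first run-in and carries a higher DS-1594b dose, yet its row does not say whether these footnotes apply.

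The Table 1 problem is a separate defect and affects Cohort C only. A primary efficacy endpoint should have one definition. Here the objectives table gives one treatment and population, and the statistical section gives another.

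**Working it through.** **1. Dose Level 1, side by side**

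| Place | Backbone at Dose Level 1 |
|---|---|
| Table 6 | not applicable for azacitidine and for venetoclax; no footnotes |
| Table 7 | not applicable for mini-HCVD |
| Section 3.3 | combination judged safe, DS-1594b dose raised, run-in repeated |
| Section 3.3, evaluability | at least 75% of the doses of DS-1594b and of the backbone drugs in Cycle 1, with no exception by level |
| Section 5.4.1, azacitidine text | given in every cycle, no exception by level |
| Sections 5.5.1–5.5.2 | mini-hyper-CVD given with DS-1594b, no exception by level |
| Table 34 | azacitidine and venetoclax rows for all of Cohort C |

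The two dose-level tables stand alone against the rest.

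**2. How many subjects this concerns (Section 3.3)**

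- Both run-ins pass: 6 at level 0, then 6 + 20 = 26 at level 1. Total 6 + 26 = 32, which reproduces the plan's figure. Share 26/32 = 81%.
- Level 0 passes and level 1 fails (2 or more of 6 with a DLT): 6 + 20 = 26 at level 0 and 6 at level 1. Share 6/32 = 19%.
- Level 0 fails: none at level 1.

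Early stopping under Section 9.3 can lower these numbers.

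**3. How likely the planned path is**

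The documents give no expected DLT rates for the combinations, so the rates below are assumptions. A run-in of 6 passes with probability P(X ≤ 1) = (1−p)⁶ + 6p(1−p)⁵. For p = 0.10 this is 0.531 + 0.354 = 0.886. For p = 0.05, 0.20 and 0.30 it is 0.967, 0.655 and 0.420. The chance that 26 subjects reach Dose Level 1, before any Section 9.3 stopping, is the product for the two levels:

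| DLT rate, level 0 / level 1 | Probability |
|---|---|
| 0.05 / 0.10 | 0.857 |
| 0.10 / 0.10 | 0.785 |
| 0.10 / 0.20 | 0.580 |
| 0.20 / 0.20 | 0.429 |
| 0.30 / 0.30 | 0.177 |

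**4. Cohort C primary efficacy endpoint, side by side**

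| Place | Treatment | Population | Window |
|---|---|---|---|
| Table 1, Cohort C objective | combination | MLLr or NPM1m | not stated |
| Table 1, Cohort C efficacy endpoint | monotherapy | MLLr | not stated |
| Table 1, Cohort A efficacy endpoint | monotherapy | MLLr | not stated |
| Section 3.3 | combination | NPM1m or MLLr | 3 months, stated for CRc |
| Section 9, cohort list | combination | R/R AML | 3 months |
| Section 9.2 (Cohorts A–C together) | not named | MLLr or NPM1m | 3 months |

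The Cohort C efficacy wording is the Cohort A wording. The safety endpoint in the same cell does say combination.

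**5. Statistical figures**

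The total reproduces: 66 + 2 × 26 + 2 × 32 = 182. With the beta(0.5, 0.5) prior, the 95% credible interval for 11/26 is (25.0%, 61.3%), as stated. The Table 22 boundaries reproduce: futility at 1, 2, 4 and 6 responses, toxicity at 4, 5, 6 and 8 DLTs. So do the early-stopping probabilities in Tables 23 and 24, for example 0.0811 at a 0.4 response rate and 0.2509 at a 0.2 DLT rate. None of these uses the cells in question.

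**The case against.** The strongest reply is that the rest of the protocol makes the intention clear. Azacitidine is described for every cycle, venetoclax and azacitidine have rows for all Cohort C subjects in Table 34, and Sections 5.5.1–5.5.2 set out mini-HCVD without mentioning dose levels. DLT evaluability depends on backbone doses. Only DS-1594b varies across the levels, so the disputed cells may have been meant as no change to the backbone. This stands as an argument about consequences. A reader might infer that 81% of each combination cohort would receive DS-1594b alone, but the documents taken together do not support that. The argument does not remove the contradiction. Neither table states the no-change meaning, the other two levels list the backbone explicitly, and the status of footnotes a to d at Dose Level 1 stays open.

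On Table 1, a reader might infer that NPM1m subjects would drop out of Cohort C's primary analysis. The analysis text says otherwise: the efficacy set in Section 9.4.1.1 includes subjects with MLLr or NPM1m, Section 9.2 covers both, and the response definition in Section 9.3 has no MLLr restriction. The endpoint wording looks like a phrase carried over from the Cohort A row. It is still the stated primary endpoint in the objectives table, and it is still wrong against its own row.

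**Conclusion.** The concern holds as two internal contradictions in current text.

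- **Tables 6 and 7 against Section 3.3.** The treatment instruction at Dose Level 1 is contradictory in both combination cohorts. It concerns 26 of 32 subjects per cohort only if at most 1 of 6 has a DLT at both levels; otherwise 6 or 0. A combined figure of 2 × 26 = 52 would need both cohorts to pass both run-ins and neither to stop early, so it should not be quoted as fixed.
- **Table 1 against its own objective and Sections 3.3, 9 and 9.2.** Cohort C's primary efficacy endpoint is misstated as to treatment and population. The dose-level counts do not measure this error.

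No sample size, boundary, operating characteristic or credible interval changes. The point is worth correcting because it touches a treatment table and a primary endpoint definition.

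**What to change.** Correct four cells: two in Table 6, one in Table 7 and one in Table 1.

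1. The sponsor should reconcile the Dose Level 1 rows of Tables 6 and 7 with Section 3.3. The rows should state what applies to the backbone at that level and, in Table 6, whether footnotes a to d apply. The content is for the sponsor and the Safety Review Committee; no regimen or dose is proposed here.
2. Align the Cohort C efficacy endpoint in Table 1 with its own objective and with Sections 9 and 9.2: rate of CR + CRh within 3 months of starting therapy, with DS-1594b in combination with azacitidine and venetoclax, in R/R AML with MLLr or NPM1m. Section 9.2 supplies the window and the population. The combination comes from the Table 1 objective, Section 3.3 and the cohort list in Section 9, because Section 9.2 does not name it. The other Phase 2 rows of Table 1 also leave out the 3-month window, which could be added at the same time.

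The cost is a text edit. The design and the analysis stay as they are.

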#### **Venetoclax:**

a During Cycle 1, venetoclax administered orally will be dose escalated daily to the goal dose of 400mg daily. Subjects will receive 100mg on Day 1, 200mg on Day 2 and 400mg on Day 3 and onwards, or adjusted ramp up per drug label if on concomitant azoles. The goal is to administer 28 days of venetoclax in Cycle 1 unless marrow remission with concomitant marrow hypocellularity and/or myelosuppression is confirmed earlier than Cycle 1 Day 28. In this case the venetoclax may be stopped earlier to avoid venetoclax related myelosuppression or further marrow hypo/aplasia after discussion and approval from the PI. Venetoclax dose ramp-up as described in Section 5.4.2

b If a bone marrow remission (<5% blasts) or aplasia/hypoplasia (<10% cellularity or insufficient sample) is not confirmed on the Day 21 bone marrow, subjects should continue venetoclax until day 28 and have a repeat bone marrow on Day 28 (+/- 5 days). If the Day 28 bone marrow shows ≥ 5% blasts proceed with cycle 2 if this is in the best interest of the subject (those with C1D28

bone marrow  $\geq 5\%$  are allowed to receive 21 days of venetoclax in Cycle 2 after discussion and approval from the PI). If the Day 28 bone marrow shows  $< 5\%$  blasts or aplasia/hypoplasia follow steps outlined in the Azacitidine administration information “a” and “b” below.

c Venetoclax will be administered orally daily on Days 1 to 28 of the first cycle; and may be reduced to Venetoclax Days 1 to 21 or less for subsequent cycles after PI approval.

d Results from published in vitro and clinical DDI studies revealed a need to modify the dose of venetoclax when it is co-administered with moderate or strong CYP3A inhibitors or P-gp inhibitors (VENCLEXTA® USPI). Based on in vitro assessment, DS-1594b has the potential to inhibit CYP3A-mediated metabolism and P-gp mediated transport of venetoclax in vivo. Thus, dose level(s) of venetoclax should be recommended by the SRC based on emerging DS-1594b PK and safety data, and the dose level of venetoclax and DS-1594b may be adjusted after review of the data collected during the safety run-in evaluation.

#### **Azacitidine:**

Azacitidine (75 mg/m^2/day) will be administered subcutaneously (SQ) or intravenously (IV) for the first 7 days of every cycle. Azacitidine may be given in a 5on - 2off - 2on or 4on - 2off - 3 on or other similar modified schedule if the subject is not able to get weekend infusions. Azacitidine is administered in the clinic or chemotherapy administration area. Both SQ and IV forms of administration are FDA approved and are allowed and considered interchangeable. Subjects may start receiving azacitidine by one route and change to the other, and administration schedules from one schedule and change to the other at any time as needed based on subject and/or physician preference.

- In Cycle 1, subjects should undergo a bone marrow aspiration and biopsy on Day 21 (+/- 4 days). Subjects who achieve a confirmed marrow remission (i.e. bone marrow blasts  $< 5\%$  by morphology) or marrow aplasia/hypoplasia ( $\leq 10\%$  cellularity or insufficient sample) may discontinue venetoclax for the remainder of the cycle and be monitored for count recovery.
  - If the Day 21 bone marrow shows  $< 5\%$  blasts, the venetoclax may be held, and consider delaying cycle 2 till ANC  $> 0.5 \times 10^9/L$  and platelets are  $> 30 \times 10^9/L$  without platelet transfusion support for  $> 5$  days.
  - If the Day 21 bone marrow shows aplasia/hypoplasia ( $\leq 10\%$  cellularity or insufficient sample), the venetoclax may be held on Day 21 to avoid venetoclax related myelosuppression or further marrow hypo/aplasia, and a repeat bone marrow should be performed on Day 28 (+/- 4 days) to confirm response and MRD assessment. If the Day 28 bone marrow shows  $\geq 5\%$  blasts, proceed with Cycle 2 if this is in the best interest of the subject (those with C1D28 bone marrow  $\geq 5\%$  are allowed to receive 21 days of venetoclax in Cycle 2). If the Day 28 bone marrow shows  $< 5\%$  blasts, the venetoclax may be continued to be held, and consider delaying cycle 2 till ANC  $> 0.5 \times 10^9/L$  and platelets are  $> 30 \times 10^9/L$  without platelet transfusion support for  $> 5$  days. If the Day 28 bone marrow shows persistent aplasia/hypoplasia ( $\leq 10\%$  cellularity or insufficient sample) venetoclax may be held to avoid venetoclax related myelosuppression or further

marrow hypo/aplasia and consider repeating a bone marrow in approximately 10-14 days.

- If a bone marrow remission (< 5% blasts) or aplasia/hypoplasia is not noted on the Day 21 bone marrow, subjects should continue venetoclax until day 28 and have a repeat bone marrow on Day 28 (+/- 5 days). If the Day 28 bone marrow shows  $\geq 5\%$  blasts proceed with Cycle 2 if this is in the best interest of the subject (those with C1D28 bone marrow  $\geq 5\%$  are allowed to receive 21 days of venetoclax in Cycle 2 after discussion with and approval from the PI). If the Day 28 bone marrow shows < 5% blasts or aplasia/hypoplasia follow steps outlined in “a” and “b” above.
- Treatment interruptions and dosing schedules other than the ones mentioned above can be considered after discussion with the PI and proper documentation of the rationale.
- DS-1594b administration will continue as scheduled and will not be impacted or adjusted based on venetoclax dosing schema or venetoclax-related delays.
- Physicians should leukoreduce with hydroxyurea to reduce the peripheral white blood count to below  $10 \times 10^9/L$  prior to the administration of the first dose of venetoclax. If the WBC is more than  $10 \times 10^9/L$ , the venetoclax should not be initiated till the white count is brought down to below  $10 \times 10^9/L$ .
- The subject will be admitted to the hospital for at least the first 7 days of the 1st cycle of concomitant azacitidine-venetoclax-DS-1594b therapy (e.g., Day 1 through Day 7) of Cycle 1, potentially admission will be longer if we encounter TLS, infections or other complications that would be better managed in the in-patient setting. To mitigate the risk for tumor lysis syndrome, subjects must be receiving tumor lysis prophylaxis, including hydration (oral, intravenous) and treatment with a uric acid reducing agent (allopurinol, rasburicase) prior to the start of venetoclax therapy and continued during Cycle 1.
  - TLS chemistry tests (potassium, uric acid, creatinine, calcium and phosphorus) will be obtained prior to dosing and 5 to 8 hours after each new venetoclax dose during the venetoclax ramp-up period. TLS chemistry test results will be reviewed by the investigator in real time and prior to the subject receiving the next higher dose of venetoclax to ensure appropriate and timely management. If a subject meets the criteria for clinically significant laboratory or clinical TLS, no additional venetoclax should be administered until resolution of the TLS. Venetoclax interruption for up to 72 hours following transient (< 48 hours) chemical changes and laboratory TLS will be allowed and will not require a dose reduction.
- See Section 6.4 for details of TLS management.
- If azacitidine cycles are delayed, venetoclax therapy may continue on Days 1-21 or Days 1-28 of a 4-week cycle after discussion with the PI or Co-PI and documentation in the medical record. If azacitidine cycles are delayed, DS-1594b may continue without

interruption after discussion with the PI or Co-PI and Sponsor, and documentation in the medical record.

